### 7.2.3 Withdrawal of Patients

Patients/caregivers will be informed that they have the right to withdraw from the study at any time, without prejudice to their medical care, and that they are not obliged to state their reasons.

Any withdrawal, and reasons for withdrawal, must be fully documented in the electronic case report form (eCRF) and source documents and the patient followed by the investigator/investigative staff. Even after the study is completed at the Follow-up Visit, the investigator/investigative staff will, regardless of reason for withdrawal, record any patient data they receive concerning SAEs, and all drug-related non-serious AEs, and subsequently report these to Albireo. Withdrawn patients will not be replaced.

Patients will be withdrawn in the following circumstances:

- A patient's/caregiver's desire for withdrawal for any reason
- Lost to follow-up (every effort must be made to contact the patient/caregiver; a certified letter must be sent)
- An AE that, in the opinion of the investigator, necessitates withdrawal
- A worsening of the symptoms related to diarrhea occurs
- Death
- Patient/caregiver estimation of lack of improvement/intolerable symptoms
- A patient's/caregiver's substantial noncompliance (eDiary and study drug compliance) or protocol violation
- An investigator's opinion that continuing the patient in the study is not appropriate. The investigator may withdraw a patient at any time, if it is considered to be in the patient's best interest

A patient who prematurely withdraws due to no improvement/intolerable symptoms, and has completed at least 12 weeks treatment in the double-blind study, will be offered the opportunity to enter open-label Study A4250-008. A patient who withdraws from treatment prematurely and will not enter Study A4250-008 will be requested to complete all visits and safety assessments per the current protocol (A4250-005). As a minimum, patients will have EOT (Visit 9) assessments at the time of withdrawal and a follow-up assessment (Visit 10) 28 days following the last dose of study drug, and the patient will be recorded as withdrawn.

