#### **8.4 Procedure for Breaking the Randomization Code**

Should a situation arise where unblinding is urgently required, i.e., only where knowledge of the study drug is required to adequately manage a life-threatening situation, the investigator at that study site may perform immediate unblinding through IWRS. The investigator should make every effort to discuss the rationale for emergency unblinding with the sponsor Medical Monitor or the ██████████ Medical Monitor prior to unblinding the individual patient.

The study site investigator and appropriate ██████████ project team members will be authorized to access the emergency unblinding functionality within the IWRS. Emergency unblinding takes place in the IWRS via a dedicated emergency unblinding module. The system will require the user to enter their emergency unblinding, which is typically provided at the same time login credentials are distributed. The exact description of the treatment assigned to the individual patient then will be accessible to the user. Once the randomization code is broken for a patient, he/she must be withdrawn from the study and all assessments and procedures at EOT should be performed. As a follow-up, Visit 10 will be performed according to the time schedule. Once a randomization code has been broken, the investigator must inform the ██████████ and sponsor Medical Monitor in writing within 24 hours. In case of technical issues accessing the system online, please see the IWRS site user manual for country specific contact telephone numbers to the ██████████ HelpDesk 24/7 system support.

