##### **Full Analysis Set**

The full analysis set (FAS) will consist of all randomized patients who received at least 1 dose of assigned treatment. Patients will be analyzed in the treatment group they were randomized to even if they received incorrect study drug. The FAS will be the primary analysis set for efficacy analyses.

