##### **Per Protocol Analysis Set**

The per protocol (PP) analysis set is a subset of the FAS, and will consist of all randomized patients for whom no major protocol violation (no violation which may affect the study efficacy outcome) is documented. The PP analysis set will provide supportive data for the efficacy analyses.

Allocation of patients to the PP analysis set will be performed before unblinding of the study.

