## 13 QUALITY CONTROL AND QUALITY ASSURANCE

### 13.1 Conduct of the Study

Albireo/██████ shall implement and maintain quality control and quality assurance procedures with written standard operating procedures to ensure that the study is conducted and data are generated, documented, and reported in compliance with the protocol, ICH GCP and applicable regulatory requirements.

This study shall be conducted in accordance with the provisions of the Declaration of Helsinki (October 1996) and all revisions thereof, and in accordance with United States Food and Drug Administration (FDA) regulations (Code of Federal Regulations, Sections 312.50 and 312.56) and with ICH GCP (CPMP 135/95).

The investigator may not deviate from the protocol without a formal protocol amendment having been established and approved by an appropriate competent authority and IEC/IRB, except when necessary to eliminate immediate hazards to the patient or when the change(s) involve(s) only logistical or administrative aspects of the study. Any deviations may result in the patient having to be withdrawn from the study and render that patient non-evaluable.

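### Withdrawal from the study for noncompliance, protocol violation or a code break leaves Week 22 and 24 outcomes unassured in patients whom the Full Analysis Set is meant to keep

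*Protocol*

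**What the plan says.** Three places in the protocol lead to withdrawal for reasons of conduct.

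- Section 7.2.3 gives a list of circumstances in which patients will be withdrawn. One entry is "substantial noncompliance (eDiary and study drug compliance) or protocol violation" on the part of the patient or caregiver.
- Section 8.4 says: "Once the randomization code is broken for a patient, he/she must be withdrawn from the study". It then names the end-of-treatment (EOT) assessments and Visit 10, and no other visits. A code break is permitted "only where knowledge of the study drug is required to adequately manage a life-threatening situation".
- Section 13.1 says: "Any deviations may result in the patient having to be withdrawn from the study and render that patient non-evaluable".

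The statistical sections take a different line. Section 11.2.1 puts every randomized patient who took at least one dose into the FAS, analyzed as randomized: "The FAS will be the primary analysis set for efficacy analyses". Major violators are removed only from the PP set: "The PP analysis set will provide supportive data for the efficacy analyses". Section 11.2.2.8 plans to tabulate patients with compliance below 80%.

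On follow-up, 7.2.3 says that a patient who withdraws from treatment early and does not enter Study A4250-008 "will be requested to complete all visits and safety assessments per the current protocol (A4250-005"). As a minimum it sets EOT assessments at the time of withdrawal and Visit 10, 28 days after the last dose. Section 11.2.2.2 plans continued efficacy collection after treatment discontinuation and assigns those data to a sensitivity analysis. The primary mixed models use observed cases.

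**The concern.** The protocol does not keep two events apart: stopping study drug and leaving the study. The list in 7.2.3 also contains death and loss to follow-up, so it reads as a list of reasons for leaving the study, not only for stopping treatment. Section 8.4 says so outright. The request for full follow-up, and the continued collection in 11.2.2.2, are worded for patients who stop treatment. Whether they cover a patient whom the investigator removes for poor diary completion, for a violation or after unblinding is left open.

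The primary endpoints need data late in the treatment period. The serum bile acid (s-BA) end value is the mean of Weeks 22 and 24, and the pruritus contrast is at Week 24. A patient removed earlier, with only the minimum follow-up, supplies neither. Diary and dosing lapses can depend on how the child is doing, so such losses may be related to outcome. The protocol would be creating missing data that it could avoid, in patients whom the FAS is there to retain. A later analysis plan cannot recover outcomes that were never collected.

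**Working it through.** **Where the guaranteed minimum ends.** Visit 10 falls 28 days after the last dose. Week 22 is Day 154 and Week 24 is Day 168 (Table 1).

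- Visit 10 precedes Day 154 whenever the last dose is before Day 154 − 28 = 126.
- Visit 10 precedes Day 168 whenever the last dose is before Day 168 − 28 = 140.

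So, apart from visit windows of ±3 days, a patient withdrawn before about Week 18 can complete everything guaranteed by 7.2.3, or everything named in 8.4, before the first of the two s-BA end samples is due. The EOT visit does not close this gap, because for a withdrawn patient it takes place at withdrawal.

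**Reproducing the stated power.** Inputs from section 11.1: 20 per group, one-sided alpha 0.0125, responder rates 60% and 10%, pruritus difference 1.0 with SD 0.95. Stated power is 84% and 83%.

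- Responder: sum of Bin(x; n, 0.60) × Bin(y; n, 0.10) over all tables with one-sided Fisher exact p ≤ 0.0125. At n = 20 this gives 84.6%.
- Pruritus: two-sample t-test with 2n − 2 degrees of freedom and noncentrality 1.0 / (0.95 × √(2/n)). At n = 20 this is 1.0 / 0.300 = 3.33 on 38 df, giving 83.6%.

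Both agree with the protocol.

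**Illustration under assumed loss.** The protocol gives no withdrawal rate. The same formulas with 0 to 3 of 20 patients per arm lacking Week 24 data give:

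| Lost per arm (assumed) | n | Responder power | Pruritus power |
|---|---|---|---|
| 0 | 20 | 84.6% | 83.6% |
| 1 | 19 | 81.0% | 81.3% |
| 2 | 18 | 76.7% | 78.8% |
| 3 | 17 | 71.8% | 76.0% |

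If equal shares per arm are instead counted as non-responders, as in the planned Cochran-Mantel-Haenszel analysis, a 10% loss turns 60% versus 10% into 54% versus 9%. The difference falls from 50 to 45 points and Fisher power to 75.8%.

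**Enrolment margin.** Section 11.1 aims for 60 to 70 patients to obtain 60 evaluable. At the upper end this covers (70 − 60)/70 = 14% loss. It protects precision, not balance, if the loss is related to outcome.

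**The case against.** The case against is substantial, and much of it stands.

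- Follow-up is planned. Section 7.2.3 requests all visits after withdrawal from treatment, and 11.2.2.2 provides for continued efficacy collection. A reader might infer that withdrawn patients lose their Week 24 data as a rule. The documents do not say that; they only fail to assure the data.
- The triggers are narrower than they look. In 7.2.3 the word substantial may govern protocol violation as well as noncompliance. Section 13.1 says may, not must. Code breaks are confined to life-threatening situations and should be few. Under 8.5 a day with both diary entries missing leads to a telephone call, not to removal.
- FAS membership is not lost. A withdrawn patient remains in the FAS, and the earlier visits enter the repeated-measures models. To call the result a per-protocol analysis under another name would be wrong.
- Missing data are addressed. Pattern mixture and tipping point analyses are planned, as are a Cochran-Mantel-Haenszel test with dropouts as non-responders and a replacement method to be prespecified in the SAP.

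A reader might also infer that bias is built into both primary endpoints. It can be made to look so. If 3 of 20 A4250 patients with an assumed change of −0.6 are removed and no placebo patients, the observed A4250 mean becomes (−1.6 × 20 + 0.6 × 3)/17 = −1.78, which overstates the assumed difference of 1.0 by about 18%. But that rests on a chosen number, a chosen outcome and removal from one arm only, before any correction by the mixed model. An equal shift of 0.18 in the placebo mean would cancel it.

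These points do not settle what happens to a patient removed from the study, as opposed to one who stops treatment. Sensitivity analyses examine the loss; they do not prevent it.

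**Conclusion.** The point holds as an inconsistency with a practical consequence. Sections 7.2.3, 8.4 and 13.1 make conduct-related events grounds for leaving the study. The FAS, the PP set, the compliance table and the continued efficacy collection in 11.2.2.2 all presuppose that such patients stay under observation. The non-evaluable status in 13.1 has no place in an FAS analyzed as randomized. The guaranteed follow-up can end before Week 22, so the affected patients are not assured a value for either primary endpoint.

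The consequence is a risk of avoidable, possibly outcome-related missing data. Neither its size nor its direction is shown, because the protocol gives no withdrawal rate and no difference between arms. The power figures illustrate loss of precision under assumed loss from 20 per arm, part of which enrolment up to 70 would absorb. Because the remedy is wording only, the change should be made.

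**What to change.** Reconcile sections 7.2.3, 8.4, 13.1 and 11.2.2.2 as follows.

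- Define leaving the study and stopping study drug as separate events, and use the terms consistently.
- State that noncompliance, protocol violation or unblinding is not by itself a reason to end scheduled visits, s-BA sampling or eDiary collection through Week 24.
- Say explicitly that the all-visits request in 7.2.3 and the continued collection in 11.2.2.2 cover these patients, and align 8.4 with them.
- Delete from 13.1 the clause that makes a patient with a deviation non-evaluable. Keep such patients in the FAS and handle them through the PP set already defined.
- Flag ratings made after a code break, for a sensitivity analysis.

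Nothing here changes, or proposes anything on, the rules for stopping or continuing study drug.

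The cost is amended wording in four sections, with no extra patients and no visits beyond the present schedule. The price in data quality is somewhat noisier data from poorly compliant families and a few caregiver ratings made after unblinding.

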### **Treatment Period**

Eligibility for randomization will be determined at Visit 3 using the pruritus (scratching reports from the Albireo ObsRO) data in the 2 weeks before Visit 3, genetic confirmation of diagnosis, and the liver biochemistry evaluations from the previous screening visits. Two weeks after Visit 3, there will be a telephone contact with the caregiver/patient to evaluate any AEs.

[figure not shown]
The patient will return to the clinic at Visit 4, Visit 5, Visit 6, Visit 7, Visit 8, and Visit 9 for assessments. If a new caregiver will begin to complete the Albireo ObsRO during the course of the trial, they will be provided with training during a clinic visit before they begin to use the eDiary. Additionally, caregivers/patients will be requested to use the diary to report the date and time each dose of study drug is administered during the Treatment Period.

The last dose of study drug will be administered the day before Visit 9. At study Visit 9, the patient has the option to enroll in an open-label extension study (A4250-008) should they meet the required entry criteria. If the patient is continuing into Study A4250-008 this will be

the last visit in this study and the first visit in Study A4250-008. Visit 9/EOT should also be performed at the time patients are prematurely withdrawn from the study.

Clinic Visit 10 will take place 28 days after Visit 9 for all patients not continuing into Study A4250-008.

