Visits	Clinic Visit 1	Clinic Visit 2	Clinic Visit 3	n/a	Clinic Visit 4	Clinic Visit 5	Clinic Visit 6	Clinic Visit 7	Clinic Visit 8	Clinic Visit 9/EOT a	Clinic Visit 10 b
Adverse events m	Continuous collection										
Study drug compliance				X	X	X	X	X	X	X	

AFP: alfa-fetoprotein; BMI: body mass index; eCRF: electronic case report form; eDiary: electronic diary; EOT: End of Treatment; ICF: informed consent form; INR: international normalized ratio; p-C4: plasma 7 $\alpha$  Hydroxy 4-cholesten-3-one; PedsQL: Pediatric Quality of Life Inventory; QoL: quality of life; RR: respiratory rate; s-BA: serum bile acid.

- a Must also be performed at the time a patient is prematurely withdrawn from the study. This visit is the same as Visit 1 in the extension protocol (Study A4250-008).
- b Assessments must be performed 28 days following the final dose of study drug. This visit is omitted if patients are entering Study A4250-008.
- c The ICF (and assent) must be signed before any study procedures are performed.
- d Past (within 1 month prior to Visit 1) and current medication will be documented in the eCRF.
- e Blood sample for genetic testing will be drawn for all patients. Genetic analysis will only be performed on a patient’s extracted DNA if previous the clinical genetic result is equivocal, unavailable, or unobtainable.
- f Includes blood pressure, pulse, RR, temperature, height (or length depending on age), and body weight (using a certified weight scale). BMI will be calculated.
- g Includes training on use of the device at Screening (Visit 1) and review of patient daily entries during 14 days prior to Clinic Visit 3 to determine eligibility.
- h See [Table 3](#) for detailed parameters.
- i Patients will fast (water intake only is permissible) for at least 4 hours prior to the collection of samples for s-BA. Exceptions can be made for infants, less than 12 months of age, if unable to fast for the full 4 hours. All s-BA results during the treatment period and follow-up will be blinded.
- j Samples will not be collected for patients  $\leq 10$  kg.
- k For girls who have reached menarche. Serum test at Visit 1; urine test at other visits. A serum pregnancy test will also be conducted at Visit 9 for patients entering Study A4250-008. If a urine pregnancy test is positive, a serum pregnancy test should be performed to confirm the pregnancy.

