#### **11.2.2.2 Missing Data**

For efficacy variables, with repeated measures, a mixed model will be employed with no additional imputation for missing values, i.e., based on “observed cases”, except where otherwise specified.

Follow-up and continued collection of efficacy data for patients who discontinue treatment will be made. These data will be included in the sensitivity analysis for primary endpoints estimating a treatment effect taking loss of effect after discontinuation into account. Because complete follow-up of all patients discontinuing treatment may not be possible, a method to replace missing data for patients who discontinue the study will be prespecified (in the SAP) taking into account loss of effect after discontinuation (for example multiple imputation).

No other replacement of missing values will be planned.

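### Off-treatment efficacy data promised in Section 11.2.2.2 are not secured at Week 24, because Visit 9 is performed at withdrawal and no separate Day 168 assessment is defined

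*Protocol*

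**What the plan says.** Section 11.2.2.2 (Missing Data) states without condition that efficacy data will go on being collected from patients who discontinue treatment. It gives their purpose: "These data will be included in the sensitivity analysis for primary endpoints estimating a treatment effect taking loss of effect after discontinuation into account". It then allows that follow-up may not be complete for everyone and leaves the replacement method to the SAP.

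Section 7.2.3 (Withdrawal of Patients) sets the request: "A patient who withdraws from treatment prematurely and will not enter Study A4250-008 will be requested to complete all visits and safety assessments", as laid down in the current protocol. The next sentence sets a floor, in which Visit 10 is timed from the final intake of study drug and the patient counts as withdrawn: "As a minimum, patients will have EOT (Visit 9) assessments at the time of withdrawal and a follow-up assessment (Visit 10) 28 days following".

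Visit 9 has two roles. It is the Day 168 visit, and in Section 7.1.1 (Treatment Period) "Visit 9/EOT should also be performed at the time patients are prematurely withdrawn from the study". Footnote a of Table 1 repeats this: "Must also be performed at the time a patient is prematurely withdrawn from the study". The Visit 9 procedure list in Section 7.1.3.2 does the same.

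Three places end study participation itself:
- Section 7.2.3 lists substantial noncompliance (including with the eDiary) and protocol violation among the grounds for withdrawal.
- Section 8.4: "Once the randomization code is broken for a patient, he/she must be withdrawn from the study", followed by the EOT procedures and Visit 10.
- Section 13.1: "Any deviations may result in the patient having to be withdrawn from the study and render that patient non-evaluable".

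Section 11.2.1 defines the full analysis set (FAS) as every randomized patient with at least one dose. Patients with major violations are left out only of the per protocol (PP) set.

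**The concern.** The loss-of-effect analysis needs Week 22 and Week 24 s-BA values and a Week 24 14-day scratching score from patients who are off drug. A site that follows the conduct sections can comply fully and still not obtain them. Once Visit 9 has been done at withdrawal, nothing tells the site to do a Day 168 assessment, and the floor in Section 7.2.3 is met about four weeks after the last dose.

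Patients stop for reasons likely to be related to treatment and outcome, such as lack of improvement, intolerable symptoms or adverse events, so the resulting gaps are likely to be informative. An SAP can say how to impute a missing value, but it cannot recover a sample or diary entry that was never taken. Withdrawing a patient for poor eDiary compliance also turns partly missing scratching data into wholly missing data for someone who stays in the FAS.

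**Working it through.** **1. Timeline on the minimum path.** Take a patient who stops drug on Day 60 and does not enter A4250-008. Day 60 is an illustrative choice.
- Visit 9/EOT: about Day 60.
- Visit 10: 60 + 28 = about Day 88.
- Scheduled Week 22 visit (Visit 8): Day 154, which is 154 - 88 = 66 days after the last required contact.
- Scheduled Week 24 visit (Visit 9): Day 168, which is 168 - 88 = 80 days after it.

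Section 9.1.1 defines the s-BA end value as the mean of Weeks 22 and 24. The minimum path supplies neither.

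**2. Timeline on the full request.** The same patient, asked for all visits, still has Visits 6, 7 and 8 (Days 84, 126 and 154) ahead. Section 9.2.1 draws s-BA at every visit, so a Week 22 value is requested. But Visit 9 has already taken place and Visit 10 falls at about Day 88, before Visits 7 and 8. The visits cannot be completed in numbered order, and whether Visit 9 is repeated on Day 168 is left to the site.

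**3. eDiary.** Section 9.2.2 has it completed twice daily for the whole study. Section 7.1.1 ties it to screening and the 24-week Treatment Period. Neither says what happens once a patient has stopped drug and is recorded as withdrawn.

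**4. The plan's power figures** (Section 11.1: about 20 per group, one-sided alpha 0.0125).
- s-BA responder, 60% vs 10%: exact Fisher power 84.6% (stated 84%).
- Pruritus, difference 1.0, SD 0.95: noncentral t with 38 df and noncentrality 1.0 / (0.95 x sqrt(2/20)) = 3.33 gives 83.6% (stated 83%).

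Both reproduce.

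**5. Size, for illustration.** The protocol states no dropout rate, so 10-15% is an assumption. One patient is 1/20 = 5% of an arm, and 10-15% of 20 is 2-3 patients. Two simple cases use the tests in step 4, not the planned mixed models.

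(a) The Week 24 value is missing, and n per arm falls in both arms:

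| n per arm | s-BA (Fisher) | Pruritus (t) |
|---|---|---|
| 20 | 84.6% | 83.6% |
| 18 | 76.7% | 78.8% |
| 17 | 71.8% | 76.0% |

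(b) A fraction d of active patients stop and revert to the placebo response, and all 20 per arm are analysed. The responder rate is 0.60(1 - d) + 0.10d and the pruritus difference is 1.0(1 - d):

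| d | Responder rate | s-BA power | Pruritus difference | Pruritus power |
|---|---|---|---|---|
| 10% | 55% | 74.8% | 0.90 | 74.4% |
| 15% | 52.5% | 68.9% | 0.85 | 68.9% |

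Case (b) shows no more power than case (a). Continued collection is therefore not justified by power. It is justified because the loss of effect is then observed instead of assumed.

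**The case against.** The strongest reply is that the protocol already asks for these data. The request in Section 7.2.3 is for all visits under the protocol. s-BA is drawn at every visit, Visit 8 stays within the request, and Section 9.2.2 keeps the eDiary running throughout the study. EOT plus Visit 10 is a floor beneath that request, not the plan. Section 11.2.2.2 itself foresees incomplete follow-up, and Section 11.2.2.5 adds pattern-mixture and tipping-point analyses and a Cochran-Mantel-Haenszel test that counts dropouts as non-responders. The data feed a sensitivity analysis, not the primary one. Code-break is confined to life-threatening situations, and Section 13.1 says only that withdrawal may follow a deviation.

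Most of this stands, and it rules out some stronger readings. A reader might infer that patients who stop drug are asked only for safety data, or that Week 24 data will not be obtained. The text supports neither. Nor does it support saying that the sensitivity analysis would rest almost wholly on imputation, since nobody can say from the protocol how many patients will complete the requested visits. Autotaxin and p-C4 are not Visit 9-only measures either; both are also drawn at Visit 4.

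The reply does not supply a Day 168 assessment for a patient whose Visit 9 has been performed. The caveat in Section 11.2.2.2 covers follow-up that proves impossible, whereas here the protocol's own minimum omits data that could be had.

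The file at hand is one part of a longer document and holds more than one dated text of the protocol, so it cannot be confirmed as final. The relevant sentences of Section 7.2.3 read alike in the December 2017 texts.

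**Conclusion.** The point holds in a limited form. The commitment in Section 11.2.2.2 and the conduct sections do not fit together at Week 24: collection is requested but not secured, and what to do on Day 168 is ambiguous. The withdrawal rules in Sections 7.2.3, 8.4 and 13.1 add to this by ending study participation where only drug, or PP status, need be affected.

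The size is modest and uncertain. Each patient is 5% of a 20-patient arm and withdrawn patients are not replaced, although the aim of enrolling 60 to 70 gives some cushion. The 2-3 patients per arm rest on the assumed 10-15% and on those patients following only the minimum path. The direct effect is on the sensitivity analysis of the primary endpoints. It is worth correcting because the gap is likely to be informative, cannot be repaired in the SAP and is cheap to close.

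**What to change.** Reconcile Sections 7.1.1, 7.1.3.2, 7.2.3, 8.4, 11.2.2.2, 13.1 and Table 1 footnote a as follows:
- Give the assessment at withdrawal its own label, Early Termination, distinct from the Day 168 visit.
- State that after study drug stops, fasting s-BA (including the Week 22 and Week 24 samples) and the twice-daily eDiary continue through Day 168, unless consent is withdrawn or the patient enters A4250-008.
- Keep the 28-day post-dose safety visit in addition to those visits.
- State that noncompliance, protocol violation and code-break do not by themselves end data collection.
- Remove from Section 13.1 the statement that such patients become non-evaluable; the PP set already deals with deviations.

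Whether and when drug is stopped remains with the sponsor's clinical team; the change concerns data collection only. The cost is protocol wording and one extra visit label in the eCRF and IWRS. The small downside is a few already scheduled visits and diary entries for patients no longer on drug.
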